6.1. Response Criteria: Measurement of Effect

The NCI criteria for relapse in AML and MDS will be used. Relapse following complete remission is defined as:

1. Peripheral Blood Counts: it is expected that cycles of treatment will be associated with cytopenias, however recurrent cytopenias or the appearance of blasts in the peripheral blood will warrant a bone marrow aspirate and biopsy evaluation.
2. Bone Marrow Aspirate and Biopsy: Presence of > 5% blasts not attributable to another cause (e.g., bone marrow regeneration), dysplasia in greater than 10% of any lineage with cytopenias in one or more lineages, or the presence of a cytogenetic abnormality consistent with MDS or AML.
3. Development of extramedullary disease.

7. Pharmaceutical Information

7.1. Toxicity Concerns

7.1.1. GVHD

We will monitor GVHD as there are reports that 5AC is associated with immunomodulatory effects that both enhance and inhibit GVHD.^{55;56} 5AC may aid antigen presentation which may be expected to both enhance GVHD⁵⁷ and concurrently improve any graft versus leukemic effects. (Pinto, Coral) 5AC may also enhance any anti-leukemic effects by inducing cytotoxic T lymphocytes against AML cells.⁵⁷ In contrast, there is also evidence that 5AC may inhibit T-cell proliferation and activation, resulting in inhibition of GVHD and graft versus leukemia effects.⁵⁸ Whatever the over-riding immune mechanisms of 5AC, no exacerbations of GVHD were observed in two reports of 5AC used after SCT.^{10;59} We will monitor GVHD according to institutional standards for all post-transplant patients.

7.1.2. Drug Combination

As to the safety of the combination, GM-CSF is often used as standard supportive care in patients receiving 5AC and tolerated well. Therefore, we do not expect increased toxicity from the combination. In fact, GM-CSF may mitigate the myelosuppressive effects of 5AC.

7.2. Dosing

7.2.1. 5-Azacytidine

There are no standard doses for 5AC as maintenance therapy. As primary therapy for MDS, 75mg/m² for 7 days is the approved dose. This dosing has also been studied in patients with active AML.⁴⁰ Lower doses are also being investigated. One study of MDS treatment compared three dosing schedules: 75mg/m² for 5 days, 50mg/m² for 10 days and 75mg/m² for 7 days. All three schedules produced responses, with the first schedule experiencing the least serious adverse events and the greatest response rates for both hematologic response and transfusion independence.⁶⁰ A regimen of 50mg/m² for 10 days, every 28 days is currently in use in a CALGB trial. A comparison of 10mg/m² IV daily for 10 days and 20mg/m² IV and SC for 5 days reported responses in both groups.⁶¹ As maintenance therapy, doses varying between 16-75mg/m² daily have been studied.^{10;49;62;63} 75mg/m² for seven days

was not well tolerated due to neutropenia, particularly in the older population. However a portion of patients did tolerate 75mg/m² without incident. In addition, many of these studies included patients with active or partially treated disease. Most studies suggest that cytopenias remain of concern in patients with active marrow disease. Our study proposes to treat patients who are currently in remission and we plan to use low doses of growth factors which would support the marrow and minimize this potential toxicity. Furthermore, data suggest that there is increased hypomethylation at lower doses of 5AC,⁴⁰ which may lead to increased reactivation of genes involved in differentiation. Therefore, a relatively low dose that still maintains differentiation activity would be optimal. Dose escalation and de-escalation are outlined in section 5.1 to help guide physicians and support patient safety.

7.2.2. GM-CSF

GM-CSF will be initiated at two flat doses based on weight and rounded to a standard dosing size, as done commonly in practice. Patients who weigh less than or equal to 70kg will receive 125 micrograms/day and those who weigh over 70kg will receive 250 micrograms/day. This dosing is based in part on our previous experiences in myeloid disorders using GM-CSF in combination with standard therapy in both the non-transplant^{51;64;65} and the post-transplant setting.^{66;67} Each of these studies supported the biologic activity of GM-CSF and determined that it was well tolerated. Patients will be given needle disposal boxes and instructions on how to properly dispose of the used syringes and needles. The needle box will be returned to the study research nurse for disposal through the pharmacy.

7.3. Timing of Initiation and Duration of Treatment

After SCT the majority of acute GVHD occurs within the first 60 days. To ensure patients are stable prior to initiating maintenance therapy, the study will start no sooner than after the day 60 post-transplant bone marrow biopsy results are available. As many relapses occur within the first several months,⁹ subjects must be enrolled within 185 days of transplant or chemotherapy. Treatment with 5AC and GM-CSF must then begin within 14 days of enrollment. Approximately half of relapses occur within the first year after SCT, with 80% occurring within the first two years.⁹ Accordingly, we would limit the duration of maintenance therapy to one year and follow patients for an additional two years.

7.4. 5-Azacytidine (NSC 102816)

1. Chemical Name: 4-Amino-1-β-D-ribofuranosyl-1,3,5-triazin-2(1H)-one
2. Other Names: 5-Azacytidine, 5-AZA, Mylosar7, Ladakamycin, Vidaza
3. Supply: 5AC is supplied as 100 mg of white, lyophilized powder with 100 mg of mannitol, USP in 30 ml flint vials. The contents of each vial should be dissolved in 4mL of sterile water or 0.9% sodium chloride to provide a 25 mg/ml slurry. 5AC does not go into solution but forms loose slurry when reconstituted in this fashion. *Do not inject the slurry intravenously.* Single injections should not exceed 2ml. Doses requiring larger volumes may be split into multiple injection

sites if volume to be administered is too large. Injection sites should be rotated on a daily basis.

4. **Storage and Stability:** Store un-reconstituted vials at 25 degrees C (77 degrees F); excursions permitted to 15-30 degrees C (59-86 degrees F) (See USP Controlled Room Temperature). 5AC reconstituted for subcutaneous administration may be stored for up to 1 hour at 25 degrees C (77 degrees F) or for up to 8 hours between 2-8 degrees C (36 and 46 degrees F). The constituted solutions hydrolyze at room temperature and should be used within 30 minutes for delivery of maximum potency.
5. **Route of Administration:** Route of administration is via subcutaneous or intravenous injections. Injections are to be given by trained nursing staff at each institution. Reconstituted solutions of 5AC are unstable. Upon reconstitution, the material should be injected within 30 minutes. To provide a homogeneous suspension, the contents of the syringe must be re-suspended by inverting the syringe 2-3 times and vigorously rolling the syringe between the palms for 30 seconds immediately prior to administration until a uniform, cloudy suspension is achieved.
6. **Toxicities:** Hematologic toxicities include leukopenia, neutropenia, thrombocytopenia, and anemia. GI toxicities include nausea and vomiting, diarrhea, stomatitis and mucositis. Increased liver function tests and renal tubular acidosis can be seen. Rarely, pulmonary edema, arrhythmia, pericarditis, hypotension, hepatic coma, CNS and neuromuscular toxicity have been seen. Rash, allergic reactions, fever, conjunctivitis and alopecia have also been noted. Local injection reactions are common and include burning, pain, violaceous (purple) discoloration lasting up to ten days, and persistent brown discoloration. In clinical studies, the most commonly occurring adverse reactions were nausea (71%), anemia (70%), thrombocytopenia (66%), vomiting (54%), pyrexia (52%), leucopenia (48%), diarrhea (36%), fatigue (36%), injection site erythema (35%), constipation (34%), neutropenia (32%) and ecchymosis (31%). Other adverse reactions included dizziness (19%), chest pain (16%), febrile neutropenia (16%), myalgia (16%), injection site reaction (14%) and malaise (11%). Complete and updated adverse events are available in the Investigational Drug Brochure and the IND safety letters.

7.5. GM-CSF (NCI 613795)

1. **Other names:** Leukine®, GM-CSF
2. **Classification:** Recombinant human GM-CSF produced in yeast formulation.
3. **Supply:** GM-CSF is supplied as either 250 mcg liquid vials or as 500 mcg lyophilized powder, multi dose vials.
4. **Storage:** Intact vials should be stored refrigerated at 2 – 8 C.
5. **Stability:** After reconstitution with 1 mL Sterile Water for Injection (SWFI), GM-CSF should be used immediately within 6 hours. After reconstitution with 1 mL Bacteriostatic Water for Injection (BWFI), GM-CSF is stable for up to 20 days in

vials and 14 days in syringes refrigerated at 20 – 80 C.

6. Route of Administration: Subcutaneous. Do not filter during preparation or administration.
7. Method of Preparation: GM-CSF solution can be prepared in prefilled BD syringes in the clinic for outpatients' treatment. Refrigerate prepared prefilled BD syringes at (2 - 8C) for up to 20 days.
8. Drug Ordering and Drug Accountability:
9. Patient Care : Patients will be provided a prescription for pre-filled, pre-dosed syringes for self-administration as per routine instructions (or administration on site or by provider as noted earlier). In addition, patients will be provided a needle and syringe disposal box and instructions on the proper disposal of the used needle and syringe. The needle box will be returned to the study research nurse for final disposal through the pharmacy.
10. Toxicities: GM-CSF may cause lethargy, myalgia, bone pain, anorexia, weight change, generalized skin eruptions, and flushing. These side effects are generally tolerated by patients.

8. Laboratory Correlative Studies

The bone marrow biopsy and aspirate will be performed as standard of care pre-treatment and as needed per the subject's primary oncologist. 10 ml in a sodium heparin green top of bone marrow aspirate may be obtained during each of these procedures for biologic correlative laboratory studies described below.

In order to describe changes of the clonogenic population, the putative LSC population, including changes in detectable cytogenetic abnormalities and antigen expression pattern, we will study freshly isolate cells from patient bone marrow aspirate. The 34^+ cells will be isolated by Ficoll density centrifugation separation followed by selection using anti-CD34 magnetic beads. Then analysis and sorting of cells based on expression of CD34, CD38, and Aldeflour will be performed. Sorted cells will be used for *in vivo* and *in vitro* studies of antigen expression and differentiation and for FISH analysis of cytogenetic abnormalities.

9. Statistical Methods

This is a phase II study of 5AC in combination with GM-CSF as maintenance therapy after definitive therapy with either stem cell transplant or consolidation chemotherapy in adults with poor risk Acute Myeloid Leukemia or MDS. We hypothesize that prolonged pressure on the leukemia stem cell to differentiate would eventually exhaust the leukemic clone and therefore reduce relapse rates.

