GM-CSF will be self-administered subcutaneously for days 1-10 of each 28 day cycle. For subjects unable to self-administer, GM-CSF may be administered by a caregiver or on site at Johns Hopkins or a local provider’s office. Dosing will be based on weight and rounded to a standard dosing size: patients who weigh less than or equal to 70kg will receive 125 micrograms/day and those who weigh over 70kg will receive 250 micrograms/day. Pediatric subjects will receive 125 micrograms/day regardless of weight. Subjects will be given prescriptions for pre-dosed syringes of GM-CSF. If the starting dose is not tolerated due to traditional side effects of GM-CSF, such as muscle aches and pains, bone or joint discomfort, or elevated WBC > 25,000, the drug will be held through resolution of these side effects. Patients who return to their pre-dosing baseline will re-start the GM-CSF at the next cycle start date at the next lower Dose Level (Table 3). Patients unable to tolerate the minimum dose (Dose Level -3) for 7 days due to either persistently elevated WBC or other side effects will be removed from the study.

Table 3

Dose Level	GM-CSF patients >18 years	Patients ≤ 18 years
-3	50micrograms x 7 D	50micrograms/ m ² x 7D
-2	50 micrograms x10 D	50micrograms/ m ² x 10D
-1	62.5 micrograms x 10D	62.5micrograms/ m ² x10D
0	125 micrograms (starting dose weight <70 kg) x 10D	125micrograms/ m² x10D¹
+1	250 micrograms (starting dose weight >70 kg) x 10D	

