5.6. Study Parameters

The studies planned during the patient evaluation and therapy are listed in Table 4. This represents the basic follow-up plan and this will change for a change in patient condition. Patients will be requested to maintain a diary documenting administration of drug and any symptomatology. All attempts will be made to collect all the correlative studies, however, due to laboratory constraints (weekends, holidays, laboratory emergencies or staffing difficulties) and patient constraints (related to intercurrent illnesses, transportation, or inadequate sample), some samples will not be collected or will not be suitable for evaluation. A patient will be considered suitable for evaluation independent of the availability of correlative study material. A variation, of +/- 3 days from any weekly scheduled testing and +/- 7 days for all other study visits, is permitted.

Table 4

Parameter	Pre-treatment¹	Weekly during first cycle	Day 1 of each cycle	End of Treatment
History/Physical	X		X	X
Weight	X		X	X
Performance Status	X		X	X
CBC with Differential	X	X	X	X
PT, PTT	X			
Reticulocyte Count	X			X
Comprehensive Metabolic Panel	X	X	X	X
Phosphate	X		X	X
Magnesium	X		X	X
Toxicity Notation	X	X	X	X
EKG	X			
Review diary	X		X	X
Serum HCG for applicable women only	X			

¹ Within 14 days prior to enrollment.

6. Treatment Evaluation

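### Section 7.5 item 7 lets prefilled GM-CSF syringes be kept for 20 days, but item 5 gives only 14 days for syringes prepared with bacteriostatic water

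*Combined protocol and SAP*

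**What the plan says.** Both statements stand in Section 7.5 of the combined protocol and SAP.

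- **Item 5 (Stability)** deals with reconstituted drug. For bacteriostatic water it reads "After reconstitution with 1 mL Bacteriostatic Water for Injection (BWFI), GM-CSF is stable for up to 20 days in" and then, across a page break, "vials and 14 days in syringes refrigerated". The container decides the limit: 20 days in a vial, 14 days in a syringe.
- **Item 7 (Method of Preparation)** allows filling on site: "GM-CSF solution can be prepared in prefilled BD syringes in the clinic". It then gives the storage limit: "Refrigerate prepared prefilled BD syringes at (2 - 8C) for up to 20 days". No diluent or source is named.

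Item 3 lists the supply: "GM-CSF is supplied as either 250 mcg liquid vials or as 500 mcg lyophilized powder, multi dose vials". The dosing schedule is in Section 5.1: "GM-CSF will be self-administered subcutaneously for days 1-10 of each 28 day cycle". Section 5.1 and Section 7.5 item 9 both have patients receiving pre-dosed syringes to inject at home.

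**The concern.** Item 7's figure of 20 days equals item 5's limit for vials, yet item 7 applies it to syringes. Because item 7 names no source or diluent, it also covers syringes filled from powder reconstituted with bacteriostatic water, for which item 5 gives 14 days.

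Item 7 is the working instruction for whoever fills and labels the syringes. Staff who follow it alone could put a 20-day expiry on a syringe for which the protocol supports 14. A patient could then inject, on days 15 to 20 after filling, drug that is past its stated stability. What is at stake is the quality of a self-injected study drug over up to 12 cycles, not the statistical design.

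**Working it through.** There is no sample-size or power figure to reproduce. The check compares the two limits and then asks when the difference could reach a patient.

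**Inputs**

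| Input | Value | Source |
|---|---|---|
| Limit for prepared syringes, no diluent named | 20 days | Section 7.5 item 7 |
| Limit after bacteriostatic water, vials | 20 days | Section 7.5 item 5 |
| Limit after bacteriostatic water, syringes | 14 days | Section 7.5 item 5 |
| GM-CSF dosing days per cycle | 1 to 10 | Section 5.1 |
| Day on which syringes are filled | not stated | assumption, varied below |

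**Step 1: the gap.** For bacteriostatic-water syringes, 20 - 14 = 6 days. Item 7 permits use on days 15 to 20 after filling, and item 5 does not support it.

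**Step 2: age of each syringe at use.** Suppose the whole course is filled k days before Day 1. The dose on Day d (d = 1 to 10) is given at age k + d - 1, so the oldest syringe is k + 9 days old.

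- All doses fit 14 days when k + 9 ≤ 14, that is k ≤ 5.
- All doses fit 20 days when k + 9 ≤ 20, that is k ≤ 11.
- For k from 6 to 11, item 7 permits every dose, but k - 5 of the ten are past 14 days.

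| Filled k days before Day 1 | Age at use (days) | Doses past 14 days, permitted by item 7 |
|---|---|---|
| 0 | 0 to 9 | 0 of 10 |
| 5 | 5 to 14 | 0 of 10 |
| 7 | 7 to 16 | 2 of 10 |
| 11 | 11 to 20 | 6 of 10 |

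The row k = 0 assumes filling at the visit that Table 4 in Section 5.6 schedules for "Day 1 of each cycle". The rows k = 7 and k = 11 are illustrations; the plan describes no such lead time.

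**Step 3: could k exceed 5?** Section 5.6 allows a variation of 7 days either way for visits outside the weekly testing, and Section 5.3 lets a cycle start 28 to 56 days after the previous Day 1. If syringes were filled for a planned Day 1 and kept while the start slipped by 7 days, k would be 7. The plan neither describes this nor rules it out.

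**Step 4: do held courses reach the gap?** After a hold for side effects, Section 5.1 restarts GM-CSF at the next cycle and at a lower dose level. Cycles start at least 28 days apart, so syringes left from the previous Day 1 would be at least 28 days old and past the 20-day limit as well. Only filling more than 5 days before the first dose brings days 15 to 20 into play.

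**The case against.** The strongest reply is that no affected dose can be shown. On the most natural reading, with syringes filled at the Day 1 visit, the oldest is 9 days old at use, and filling in the clinic is only permitted, not required. That stands as a limit on the size of the point. It does not remove the contradiction, because item 7 is the rule meant to govern the less natural cases and its figure disagrees with item 5.

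Two stronger readings are tempting, and the documents do not support them.

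- **Sterile water.** A reader might infer a conflict of 20 days against 6 hours, since item 5 says "After reconstitution with 1 mL Sterile Water for Injection (SWFI), GM-CSF should be used immediately within 6 hours". But item 7 does not mention sterile water, and item 5's instruction is specific. Read together, the specific limit governs, and staff told to use the product immediately have no reason to apply a general storage maximum to it.
- **Liquid vials.** A reader might infer that 20 days is also wrong for syringes filled from the liquid vials in item 3. Item 5 addresses only reconstituted drug, so for the liquid item 7 is the only statement and contradicts nothing. A protocol's drug section need not carry the stability data behind each limit.

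The inconsistency is thus confined to syringes prepared with bacteriostatic water.

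**Conclusion.** The point holds in that confined form. For bacteriostatic-water syringes, item 7 permits storage 6 days past the limit in item 5, and no other section reconciles the two. The documents do not show which figure is right; 14 days is the conservative one, and the only one tied to both a container and a diluent.

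The point is minor. A 10-day course filled between 5 days before Day 1 and Day 1 itself meets the 14-day limit. The filling date, source and diluent are not stated, so the number of affected doses is unknown and may be zero. A reader might infer that patients will inject degraded drug, or that efficacy results could suffer. The documents do not support that: they give no potency data and describe no practice that leads to use after day 14. Design, sample size, stopping rules and analysis are untouched.

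**What to change.** In Section 7.5 item 7, state 14 days at 2 to 8 °C for syringes prepared with bacteriostatic water, and allow a longer limit for another source only where pharmacy documents it. Item 5 can stay as it is.

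The cost is a line or two of pharmacy text at the next amendment. The shorter limit does not constrain a 10-day course filled on Day 1 or up to 5 days before it. A course filled earlier than that would need its last syringes replaced. Accrual, sample size and analysis do not change.

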9.1. Objectives

9.1.1. Primary Objective

The **primary objective** of the trial is to evaluate the two year relapse-free survival (RFS) of maintenance treatment with 5AC in combination with GM-CSF in patients with poor-risk Acute Myeloid Leukemia (AML) and Myelodysplasia (MDS) in

complete remission after definitive therapy with either a stem cell transplant or consolidation therapy with chemotherapy. RFS will be defined as time to relapse or death. The start time of RFS will be the date of first remission marrow following induction treatment. Patients will be required to have no morphologic evidence of leukemia or active MDS before entry onto the protocol. This study will monitor three separate cohorts:

1. Patients in complete remission (CR) following a full myeloablative stem cell transplant
2. Patients in CR following a non-myeloablative stem cell transplant
3. Patients in CR following standard consolidation therapy

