2.9. Clinical Studies with Differentiating Agents and GM-CSF

Our group has built upon such preclinical data and has focused on studying numerous agents with differentiating properties. A phase I trial of the differentiating agent Bryostatins with GM-CSF demonstrated clinical activity in refractory myeloid malignancies but was intolerable at biologically active doses.⁵¹ Subsequently, a Phase I study with MS-275 showed clinical activity and evidence of differentiation.⁴⁵ In a Phase II study of MS-275 and GM-CSF in patients with high-risk MDS or relapsed and refractory AML, 21% of patients achieved a response and demonstrated clinical evidence of differentiation.⁵² We propose a phase II study to determine the impact of maintenance therapy with 5-azacytidine and GM-CSF in patients with poor-risk AML or MDS, who are in remission after definitive treatment with either stem cell transplant or consolidation chemotherapy.

In order to precede relapse and to avoid lead time bias, treatment would need to commence within 185 days of definitive therapy. Furthermore, approximately 50% of relapses occur within the first year and up to 80% within two years after SCT, therefore we would limit the duration of maintenance therapy to one year, followed by two years of follow-up.

3. Patient Selection and Enrollment

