3.1. Inclusion Criteria

1. Age \geq 0.5 years
2. Initial diagnosis of poor -risk AML or MDS (defined in section 3.2), treated with either stem cell transplant or consolidation chemotherapy, within the past 60-185 days
3. ECOG performance status 0-2
4. No morphologic evidence of leukemia or active MDS as determined by JHH Hematopathologist independent review of a bone marrow aspirate and biopsy done following the completion of therapy.
5. Peripheral blood count recovery: Neutrophil count \geq 1000 / μ L, platelet count \geq 50x 10⁹ / μ L without platelet transfusions, and adequate hematocrit independent of red cell transfusions .
6. No evidence of extramedullary leukemia, such as CNS or soft tissue involvement
7. Adequate end organ function as measured by the following: AST and ALT \leq 4 x normal, total serum bilirubin $<$ 2 x upper limit normal (unless due to hemolysis, Gilbert's syndrome, or ineffective erythropoiesis), creatinine \leq 2 x upper limit of normal
8. Ability to give informed consent
9. In agreement to use an effective barrier method of birth control to avoid pregnancy during the study and for a minimum of 30 days after study treatment, for all male and female patients who are fertile

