3.2. Inclusion Criteria Definitions

The original diagnosis of AML or MDS must have been confirmed by bone marrow aspirate and/or biopsy review by a JHH Hematopathologist. Poor-risk AML is defined as disease that is therapy-related or arises from a previous marrow disorder, or *de novo* AML that is associated with any of the following characteristics: patient age 60 years or greater, trilineage dysplasia, disease status greater than or equal to CR2, FLT3/ITD mutations, detectable disease at time of consolidation chemotherapy or SCT, or poor-risk cytogenetics, which include abnormalities of chromosome 3, 5, or 7, trisomy 8, 11q23 abnormalities, t(6;9), 20q-, and complex karyotype.

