9.2. Study Design

This will be a three-arm phase II study with historical references for each arm. The historical two-year RFS and corresponding event rates in these arms are assumed to be: myeloablative, 40% (0.46 per person year); non-myeloablative, 34% (0.54 per person year); and standard consolidation, 20% (0.80 per person year). The non-parametric Kaplan-Meier estimate will be used to monitor the relapse-free survival function in each cohort.

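### Primary RFS starts at the first remission marrow, but patients enter only if still in remission 60-185 days after definitive therapy; ordinary Kaplan-Meier then favours the drug unless the historical values share that origin and landmark

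*Combined protocol and SAP*

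**What the plan says.** Section 9.1.1 defines RFS as time to relapse or death and fixes the origin: "The start time of RFS will be the date of first remission marrow following induction treatment". No other section defines an origin for RFS.

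Entry comes later. Section 3.1 requires that patients were "treated with either stem cell transplant or consolidation chemotherapy, within the past 60-185 days", with a marrow after therapy that shows no leukaemia or active MDS. For transplant patients, section 7.3 adds that "the study will start no sooner than after the day 60 post-transplant bone marrow biopsy results are available". It also sets the last step: "Treatment with 5AC and GM-CSF must then begin within 14 days of enrollment".

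On the estimator, section 9.2 says: "The non-parametric Kaplan-Meier estimate will be used to monitor the relapse-free survival function in each cohort". Section 9.4 uses the same estimator at one year for the interim looks. Neither section mentions delayed entry, left truncation or a landmark.

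On the comparator, section 9.2 says: "The historical two-year RFS and corresponding event rates in these arms are assumed to be: myeloablative, 40% (0.46 per person year". The other two arms have 34% (0.54) and 20% (0.80). No source, population or time origin is given.

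The only text on timing bias is in section 2.9: "In order to precede relapse and to avoid lead time bias, treatment would need to commence within 185 days of definitive therapy".

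Section 3.2 counts as poor risk patients with "disease status greater than or equal to CR2, FLT3/ITD mutations, detectable disease at time of consolidation chemotherapy or SCT", among other features.

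**The concern.** A patient whose remission was documented before enrolment had to stay alive and relapse-free until enrolment in order to be in the trial. Patients who relapsed or died in that interval are never enrolled. Starting the clock at the remission marrow credits every such patient with event-free time that eligibility guaranteed. The 185-day limit in 2.9 caps this time but does not remove it.

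The trial has no concurrent control, so the primary result is read against 40/34/20%. If those values come from patients followed from remission or transplant without a requirement to be relapse-free months later, an inactive regimen would look better than history in all three arms.

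The origin is also not fully defined. For a patient in CR2 or later, the first remission after induction may be one that has already ended in relapse. For a patient with detectable disease at transplant or consolidation, the relevant remission may be shown only afterwards. The definition does not say which remission starts the clock.

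**Working it through.** **Inputs.** Historical two-year RFS S(2) = 0.40, 0.34, 0.20 (9.2); exponential RFS (9.4); entry 60-185 days after definitive therapy (3.1); 25 patients per arm (9.4). Assumed here, because the documents are silent: entry is uniform over the window, the drug has no effect, and history is not conditioned on a landmark.

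**Plan's own rates.** h = -ln S(2)/2 gives 0.458, 0.539 and 0.805 per year, against the printed 0.46, 0.54 and 0.80. These reproduce, apart from loose rounding in the third.

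**Effect of guaranteed time.** If a patient must be event-free for a time d after the origin, apparent two-year RFS is exp(-h(2 - d)). For d uniform on (a, b), the mean is S(2) × [exp(hb) - exp(ha)] / [h(b - a)], with days divided by 365.25.

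Example, myeloablative arm, 60-185 days: a = 0.1643, b = 0.5065, exp(ha) = 1.078, exp(hb) = 1.261, h(b - a) = 0.157. The multiplier is 0.183/0.157 = 1.167, and 0.40 × 1.167 = 0.467.

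| Guaranteed event-free time | Myeloablative | Non-myeloablative | Consolidation |
|---|---|---|---|
| None (null) | 40.0% | 34.0% | 20.0% |
| Uniform 0-125 days (remission first shown at day 60 after definitive therapy) | 43.3% | 37.3% | 23.0% |
| Uniform 60-185 days (remission coincides with definitive therapy) | 46.7% | 40.8% | 26.3% |
| Same, remission 30 days earlier (90-215) | 48.5% | 42.6% | 28.1% |
| Same, remission 60 days earlier (120-245) | 50.3% | 44.6% | 30.0% |
| Single interval of 185 days | 50.4% | 44.7% | 30.1% |

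Beyond the 60-185 day case, each further 30 days adds about 1.8-2.0 points.

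**Check of remedies.** In a large-sample simulation of an inactive drug (200,000 patients, 60-185 days), two-year estimates were:

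- ordinary Kaplan-Meier from remission: 0.466/0.406/0.265;
- delayed-entry Kaplan-Meier from remission: 0.431/0.370/0.230, where theory, S(2)/S(60 days), gives 0.431/0.372/0.228;
- clock started at enrolment: 0.399/0.340/0.202.

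The enrolment clock returns the nulls, but only because the hazard is constant. Delayed entry does not return them, because nobody is at risk before day 60.

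**Scale.** The binomial standard error at the null with n = 25 is √(0.40 × 0.60/25) = 0.098, √(0.34 × 0.66/25) = 0.095 and √(0.20 × 0.80/25) = 0.080.

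**The case against.** The strongest reply is that the comparator may already be matched. Section 9.2 gives the historical values for these arms, and 9.1.1 describes the arms as patients in CR after transplant or consolidation. That may imply partial matching, and with full matching there is no inflation. This stands as a limit on the claim: a reader might infer that the estimate is shown to be inflated, and the documents do not support that. They show an uncorrected origin and an undocumented comparator. Being in CR after treatment is also not the same as being still in CR 60-185 days later.

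A second reply is that 3-7 points is less than one standard error with 25 patients. That is true, but sampling error falls either way, while this shift always favours the drug and occurs in every arm.

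Three further inferences are tempting and should not be drawn.

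- *A raised false-positive rate.* Tables 5-7 report rejection probabilities, but no section states the rule for rejecting the null, so no such rate can be derived.
- *A disabled futility rule.* One-year RFS is inflated too, but this changes little. At the plan's own hazards an inactive drug has one-year RFS of √S(2) = 63/58/45%, and the rule compares this with 40/34/20%. Near those values the printed stopping probabilities are already low (0.06 and 0.02 at 60% in Tables 5 and 6; 0.06 and 0.01 at 40% and 50% in Table 7). The one-year against two-year comparison is a separate matter.
- *Conflicting RFS clocks.* Section 5.4 sets how long patients are followed, and the accrual remark in 9.4 is a planning approximation. Only 9.1.1 defines an RFS origin.

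**Conclusion.** The concern holds in conditional form. As written, the analysis counts guaranteed event-free time as time at risk for every patient whose remission precedes entry, and nothing in the plan corrects for it. With constant hazards, no drug effect, uniform entry and unmatched history, the 40/34/20% benchmarks would appear as 43/37/23% to 47/41/26% in the two cases worked.

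The resulting 3-7 points is not an upper bound. A single interval of 185 days gives 50/45/30%, a shift of about one standard error or slightly more, and remission well before definitive therapy gives more still. A hazard that is higher early would also enlarge the shift, and 7.3 says that many relapses come in the first several months. The shift is smaller for patients whose remission is first shown near entry, and nil if history shares the origin and landmark.

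The unclear choice of remission for patients in CR2 or later, or with detectable disease at definitive therapy, needs correcting whatever the historical source turns out to be.

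**What to change.** 1. Define primary RFS as time from enrolment to relapse or death, or from cycle 1 day 1. If cycle 1 day 1 is chosen, say how enrolled patients who never start are handled. If enrolment is chosen, say how they are followed, since the clock in 5.4 starts with the first cycle. For patients who start, three years of follow-up covers two years from either origin.
2. State the source, population and time origin of the historical values. Where the source allows, use values conditional on being relapse-free at a matching landmark. Moving the trial's clock alone is not enough unless the hazard is constant. If the source does not allow it, state the limitation with a sensitivity range computed from trial patients' actual remission-to-enrolment intervals, not a fixed 3-7 points.
3. If the nulls change, reset the priors and rerun Tables 5-7.
4. If RFS from remission is also reported, define the origin as the remission that qualified the patient for entry. Use delayed-entry Kaplan-Meier with a comparator matched on the same landmark, since delayed entry alone would still show about 43/37/23% for an inactive drug.

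The cost is one changed definition, a check of the historical source and possibly a rerun of the simulations. The downside is that the historical target may rise. The documents do not show that patient-level historical data exist; without a source that allows conditioning, only the stated limitation and sensitivity range are possible. Beyond dates of remission, enrolment and first dose, no new data from trial patients are needed.
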